#### 3.5.3 Vital Signs

Vital signs parameters (heart rate, systolic and diastolic blood pressure) will be listed and summarized using descriptive statistics for each treatment group by visit.

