MSA is a severe neurodegenerative disease for which there are limitations in existing therapy. There is a scientific rationale to assess the clinical benefit of safinamide in MSA patients in this proof of concept study. The existing clinical data on safinamide derived from post marketing surveillance, and clinical studies support an overall, favorable benefit/risk profile. More detailed information about the known and expected benefits and risks as well as reasonably expected adverse events of safinamide may be found in the Investigator's Brochure.

3. Objectives and Endpoints

Objectives	Endpoints
Safety	
To evaluate the safety and tolerability of safinamide, 200 mg od, compared with placebo	 The nature, frequency, severity, relationship (to study drug), actions taken, and outcome of TEAEs and SAEs. Changes in physical and neurological examination findings. Changes in vital sign (heart rate, systolic and diastolic blood pressure) values, including occurrence of abnormalities. Changes in 12-lead ECG parameter measures, including occurrence of abnormalities. Changes in clinical chemistry and hematology values, including shifts from Baseline and occurrence of abnormalities. Number of withdrawals (and reason if given).
Efficacy	
To evaluate the potential efficacy of safinamide 200 mg od, as add-on therapy, on motor function and/or quality of life	 The change from baseline to week 12 in the goniometric measurement for "lateral" and "anterior" displacement Change from baseline at week 12 in Unified MSA Rating Scale, MSA Health-Related Quality of Life (MSA-QoL) scale, Montreal Cognitive Assessment (MoCA) scale, Unified Dystonia Rating Scale (UDRS).

4. Study Design

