9.4.1.3. Vital Signs

Values and changes from baseline will be summarized using descriptive statistics for each vital sign parameter at each visit by study intervention group.

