- Any abnormal laboratory test results (hematology, clinical chemistry, or urinalysis) or other safety assessments (eg, ECG, radiological scans, vital signs measurements), including those that worsen from baseline, considered clinically significant in the medical and scientific judgment of the investigator (ie, not related to progression of underlying disease).
- Exacerbation of a chronic or intermittent pre-existing condition including either an increase in frequency and/or intensity of the condition.
- New conditions detected or diagnosed after study intervention administration even though it may have been present before the start of the study.
- Signs, symptoms, or the clinical sequelae of a suspected drug-drug interaction.
- Signs, symptoms, or the clinical sequelae of a suspected overdose of either study intervention or a concomitant medication. Overdose per se will not be reported as an AE/SAE unless it is an intentional overdose taken with possible suicidal/self-harming intent. Such overdoses should be reported regardless of sequelae.
- "Lack of efficacy" or "failure of expected pharmacological action" per se will not be reported as an AE or SAE. Such instances will be captured in the efficacy assessments. However, the signs, symptoms, and/or clinical sequelae resulting from lack of efficacy will be reported as AE or SAE if they fulfil the definition of an AE or SAE.

Events NOT Meeting the AE Definition

- Any clinically significant abnormal laboratory findings or other abnormal safety assessments which are associated with the underlying disease, unless judged by the investigator to be more severe than expected for the participant's condition.
- The disease/disorder being studied or expected progression, signs, or symptoms of the disease/disorder being studied, unless more severe than expected for the participant's condition.
- Medical or surgical procedure (e.g., endoscopy, appendectomy): the condition that leads to the procedure is the AE.
- Situations in which an untoward medical occurrence did not occur (social and/or convenience admission to a hospital).
- Anticipated day-to-day fluctuations of pre-existing disease(s) or condition(s) present or detected at the start of the study that do not worsen.

Definition of SAE

If an event is not an AE per definition above, then it cannot be an SAE even if serious conditions are met (e.g., hospitalization for signs/symptoms of the disease under study, death due to progression of disease).

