# 2.3.2 Safety Endpoints

Safety endpoints include the following parameters:

- The nature, frequency, severity, relationship (to study drug), actions taken, and outcome of TEAEs and SAEs.
  - Adverse events will be coded using Medical Dictionary for Regulatory Activities (MedDRA) Version 23.0. The severity of AEs will be assessed using "mild", "moderate" and "severe". The degree of "relatedness" of the AE to the study treatment will be described using "related to study drug" and "not related to study drug".
  - Treatment-emergent adverse events (TEAEs) are defined as those AEs that have a start date on or after the first administration of study drug. AEs with unknown/unreported onset date will also be counted as TEAE.
- Physical and neurological examination findings.
  - Physical and neurological examinations will be performed at Screening and Week 12. Results will be recorded as "abnormal", "normal" and "not assessed".
- Vital sign (heart rate, systolic and diastolic blood pressure) values.
  - o Vital signs will be assessed at Screening, Day 1, 14, 28, 56, and Day 84/Week 12.
- 12-lead Electrocardiogram (ECG) parameter measures.
  - o 12-lead ECG will be performed at Screening and Week 12.
- Clinical chemistry and hematology values.
  - Clinical chemistry and haematology evaluations will be performed at Screening and Week 12.
- Number of withdrawals (and reason if given).
  - O Subject withdrawals from the study will be recorded on the End of Study CRF with reasons provided.

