### 3.5 Safety Assessment

Safety data will be summarized by actual treatment received (and in total for selected analyses) based on the Safety Population. Any abnormal laboratory test results or other safety assessments will be reported as AE and listed.

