### 3.5.2 Clinical Laboratory Tests

Values and changes from baseline will be summarized using descriptive statistics for each treatment group by visit for protocol-required laboratory tests in Appendix A. All lab results will be listed.

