# 5 CHANGES FROM PROTOCOL-SPECIFIED STATISTICAL ANALYSES

The "Enrolled Population" is redefined as "Screened Population"; the "Evaluable Population" is redefined as "Intent-to-Treat (ITT)" Population".

The analyses of efficacy endpoints other than MoCA will be conducted using MMRM instead of ANCOVA.

Shift tables will not be provided for safety assessments since any abnormal findings will be captured in AEs.

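### SAP 3.5.3 plans vital-sign values only, so the protocol's change-from-baseline summary is lost without being declared, and the AE route does not replace counts of abnormal readings

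*SAP*

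**What the plan says.** The protocol (section 3, Objectives and Endpoints) lists this safety endpoint: "Changes in vital sign (heart rate, systolic and diastolic blood pressure) values, including occurrence of abnormalities". Section 9.4.1.3 gives the matching analysis: "Values and changes from baseline will be summarized using descriptive statistics for each vital sign parameter at each visit by study intervention group".

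SAP 2.3.2 shortens the endpoint to "Vital sign (heart rate, systolic and diastolic blood pressure) values". SAP 3.5.3 says the three parameters "will be listed and summarized using descriptive statistics for each treatment group by visit". The section immediately before it, SAP 3.5.2 on laboratory tests, reads differently: "Values and changes from baseline will be summarized using descriptive statistics for each treatment group by visit".

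On abnormal findings, SAP 3.5 states: "Any abnormal laboratory test results or other safety assessments will be reported as AE and listed". SAP section 5, which lists changes from the protocol, adds: "Shift tables will not be provided for safety assessments since any abnormal findings will be captured in AEs". It also declares the renamed populations and the move from ANCOVA to MMRM. It does not mention vital-sign change. SAP versions 1.0 and 2.0 agree on all of this.

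**The concern.** A SAP may depart from its protocol, but it should say so. Here the departure touches an endpoint of the primary objective, and the section written to record such changes does not record it. A programmer following SAP 3.5.3 would produce no change table.

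Vital signs matter more here than in many trials. ECG and laboratory tests are taken only at screening and Week 12, while vital signs are taken at Day 1 and at Weeks 2, 4, 8 and 12. Protocol 8.4 names hypertension and postural hypotension among the possible effects of excessive MAO-B inhibition. Protocol section 2 names autonomic failure as a cardinal feature of the disease, so an abnormal blood pressure can readily be put down to the disease.

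**Working it through.** **1. The texts side by side**

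| Item | Protocol | SAP |
|---|---|---|
| Endpoint, vital signs | Change, including abnormalities (section 3) | Values (2.3.2) |
| Analysis, vital signs | Values and change by visit (9.4.1.3) | Values by visit, plus listing (3.5.3) |
| Analysis, laboratory tests | Values by visit, change to Week 12 (9.4.1.5) | Values and change by visit (3.5.2) |
| Vital-sign abnormality counts | Endpoint wording only; none in 9.4.1.3 | None; routed to AEs (3.5, section 5) |
| Departure declared | n/a | Shift tables only (section 5) |

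SAP 3.1.4, on summary statistics, contains no general rule that would add change. SAP 3.1.3 defines baseline as Day 1, when vital signs are taken, so change can be computed. Missing output: 3 parameters × 4 post-baseline visits = 12 change summaries per arm.

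**2. Sample size**

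48 at 2:1 gives 32 and 16. The plan's 40 evaluable at 2:1 gives 40 × 2/3 = 26.7 and 40 × 1/3 = 13.3, in line with the stated 26 and 14.

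**3. What the visit summaries cannot give**

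With equal SDs at both visits and baseline to follow-up correlation rho (not in the documents; assumed over a range), SD of change = SD × sqrt(2(1 − rho)):

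- rho 0.3: 1.18 SD
- rho 0.5: 1.00 SD
- rho 0.7: 0.77 SD
- rho 0.8: 0.63 SD

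The planned tables show the visit SDs but not rho, so the spread of individual change stays unknown.

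**4. Subtracting means when readings are missing**

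If a fraction m of an arm has no reading at a visit, and participants with readings differ from those without by d in Day 1 mean, then:

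follow-up mean − Day 1 mean of all = within-participant change in those with readings + m × d.

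For illustration only, take the evaluable numbers as those with readings, and d = 0.25 to 0.5 SD (assumed):

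- Safinamide: m = 6/32 = 0.1875, so m × d = 0.047 to 0.094 SD.
- Placebo: m = 2/16 = 0.125, so m × d = 0.031 to 0.063 SD.
- Arm comparison: 0.016 to 0.031 SD if d has the same sign in both arms, 0.078 to 0.156 SD if the signs are opposite.

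The artefact is modest at this level of missingness and grows in proportion to m. Missing readings are plausible. The schedule of activities allows Visits 3 to 6 by phone or video. Protocol section 8 permits the patient's own instruments at Visits 4, 5 and 6, but its Visit 3 text does not mention them.

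**5. Does the AE route capture any abnormal finding?**

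Under protocol Appendix 3, an abnormal safety assessment is an AE if it is "considered clinically significant in the medical and scientific judgment of the investigator". The same appendix excludes abnormal assessments associated with the underlying disease unless the investigator judges them worse than expected. Two groups of abnormal readings therefore never reach the AE tables: those not judged clinically significant, and those attributed to the disease at its expected severity. The reason given in SAP section 5 does not hold under the protocol's own definition.

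**The case against.** **The gap is small and largely readable from the planned tables.** Day 1 is one of the visits, so its arm means are displayed and a reader can subtract them. Individual values are listed. This stands for mean change when readings are complete. It does not supply the SD of change or matched change when readings are missing.

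**There is a second series.** UMSARS Part III records blood pressure and heart rate at rest and standing at baseline and Weeks 4, 8 and 12, and SAP 3.4.2 summarises it by arm over time. This is a fair point and covers three of the four post-baseline visits. It does not cover Week 2, and SAP 3.4.2 names no change from baseline for Part III either.

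**The SAP did not remove planned abnormality counts.** A reader might infer that it did. Protocol 9.4.1.3 plans none; abnormalities appear only in the endpoint wording. The SAP openly sends abnormal findings to AEs, which are counted by preferred term. The valid criticism is that this route is incomplete.

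**Baseline imbalance is not a reason to treat the raw means as invalid.** A reader might compute the 95% range of the chance baseline difference, 1.96 × sqrt(1/32 + 1/16) = 0.60 SD, and with an assumed systolic SD of 15 to 20 mmHg read ±9 to 12 mmHg as bias in the follow-up means. That does not follow:

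- Only rho times a baseline difference carries into raw follow-up means: ±4.5 to 6 mmHg at rho 0.5, ±6.3 to 8.4 at rho 0.7.
- Change scores leave (rho − 1) times it: the same size with opposite sign at rho 0.5, and ±2.7 to 3.6 at rho 0.7.
- The SE of the arm difference is 0.306 SD for raw values, against 0.362, 0.306 and 0.237 SD for change at rho 0.3, 0.5 and 0.7. Change is the more precise only if rho exceeds 0.5.

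The documents give neither the SD nor rho.

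**No decision rests on it.** Protocol 9.1 plans no safety test. This also stands.

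**Conclusion.** The point holds as an undeclared mismatch between protocol and SAP on a primary-objective safety endpoint. If the SAP is followed as written, 12 change summaries per arm are not produced, the SD of within-participant change is unavailable, and subtraction of visit means is not a safe substitute where readings are missing. The statement that AEs capture any abnormal finding conflicts with the protocol's AE definition, and neither document sets vital-sign limits or plans counts that would fill the gap.

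The consequence is incomplete safety reporting. No error rate changes and no formal conclusion is reversed. The case rests on the texts; the SD-of-change range assumes equal SDs and rho from 0.3 to 0.8, and the missing-data figures are illustrative. It does not rest on baseline imbalance, which change scores remove only in part. The sponsor should correct this, because the data are already collected.

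**What to change.** 1. In SAP 2.3.2 and 3.5.3, state that values and changes from baseline (Day 1) will be summarised for heart rate, systolic and diastolic pressure, by arm, at Weeks 2, 4, 8 and 12. Give the number of participants contributing to each change.
2. As a new item, not a restored one, add the number and percentage of participants per arm outside vital-sign limits that the sponsor fixes before unblinding.
3. Reword the shift-table reason in SAP section 5 so that it agrees with the AE definition in protocol Appendix 3.
4. If the sponsor declines item 1 or 2, declare and justify the omission in section 5.

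The cost is a few sentences in the SAP, extra columns in an existing table and one short count table. No new data are needed.

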#### 3.5.4 12-Lead Electrocardiograms

The overall interpretation of ECG data will be summarized by counts and percentages by treatment group. All ECG findings will be listed.

#### 3.5.5 Physical and Neurological Examinations

General physical examination and neurological examination results will be listed and summarized by counts and percentages for each treatment group at each scheduled visit.

#### 4 ANALYSIS TIMING

# 4.1 Interim Analysis

No interim analysis is planned.

## 4.2 Pre-Final Analysis

After the database is locked and exclusions from analysis populations have been finalized, the randomized treatment assignments will be unblinded and the pre-final analysis will be generated.

# 4.3 Final Analysis

After all comments on the pre-final analysis have been resolved and the study database is declared final, the final analysis will be generated. If there were no changes to the pre-final analysis or the study database, the pre-final TFLs may be considered final.

# 5 CHANGES FROM PROTOCOL-SPECIFIED STATISTICAL ANALYSES

The "Enrolled Population" is redefined as "Screened Population"; the "Evaluable Population" is redefined as "Intent-to-Treat (ITT)" Population".

The analyses of efficacy endpoints other than MoCA will be conducted using MMRM instead of ANCOVA.

Shift tables will not be provided for safety assessments since any abnormal findings will be captured in AEs.

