8.1.3. Electrocardiograms

- 12-lead ECG will be obtained as outlined in the SoA (see Section 1.3).
- ECGs will be reviewed locally, for safety findings, which should be documented by the Investigator. Paper ECGs will remain at site (as source documents).
- Results are to be documented in the eCRF as normal, or abnormal and whether clinically significant.

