8.1.4. Clinical Safety Laboratory Assessments

- See Appendix 2 for the list of clinical laboratory tests to be performed and to the SoA for the timing and frequency.
- The investigator must review the laboratory report, document this review, and record any clinically relevant changes occurring during the study in the AE section of the CRF. The laboratory reports must be filed with the source documents. Clinically significant abnormal laboratory findings are those which are not associated with the underlying disease, unless judged by the investigator to be more severe than expected for the participant's condition.
- All laboratory tests with values considered clinically significantly abnormal during participation in the study or within two (2) weeks after the last dose of study intervention should be repeated until the values return to normal or baseline or are no longer considered clinically significant by the investigator or medical monitor.
 - If such values do not return to normal/baseline within a period of time judged reasonable by the investigator, the etiology should be identified, and the sponsor notified.
 - o All protocol-required laboratory assessments, as defined in Appendix 2, must be conducted in accordance with the laboratory manual and the SoA.

 If laboratory values from non-protocol specified laboratory assessments performed at the institution's local laboratory require a change in participant management or are considered clinically significant by the investigator (e.g., SAE or AE or dose modification), then the results must be recorded in the CRF.

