9.4.1.5. Safety Laboratory Parameters

Descriptive statistics for each clinical laboratory test will be presented by study intervention group at each visit. Change from baseline to week 12 values will also be summarized.

According to laboratory normal ranges, laboratory test results will be categorized as low (< lower normal limit), normal (within normal range), and high (> upper normal limit). Shift tables

comparing the distributions of these three categories at baseline versus week 12 will be presented by treatment group for key safety laboratory evaluations.

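### The SAP drops the safety shift tables because all abnormal findings will be adverse events, but the protocol makes only some of them adverse events, so laboratory shifts go uncounted by arm

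*SAP*

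**What the plan says.** Protocol section 3 lists, under the safety objective, "Changes in clinical chemistry and hematology values, including shifts from Baseline and occurrence of abnormalities". Section 9.4.1 makes safety and tolerability the primary objective. To serve that endpoint, protocol 9.4.1.5 classifies laboratory results as low, normal or high against normal ranges. It plans shift tables by treatment group, baseline against week 12, for key tests that it does not name. Protocol 9.4.1.2 plans a similar shift table for the physical examination.

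SAP v2.0 section 5 withdraws all of these: "Shift tables will not be provided for safety assessments since any abnormal findings will be captured in AEs". SAP 3.5 states the same premise as a rule: "Any abnormal laboratory test results or other safety assessments will be reported as AE and listed". SAP v1.0 has the same sentence in section 5.

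For laboratory data, SAP 3.5.2 keeps descriptive statistics of values and changes by arm and visit, plus a listing of all results.

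**The concern.** The withdrawal is declared openly. What fails is its justification. If every abnormal result became an adverse event, the adverse event tables would hold the information and a shift table would add little. If only some do, the SAP has removed the only planned table that counts the remainder.

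What is at stake is a component of the primary objective's own endpoint. A reader of the report could not see from any table how many patients in each arm moved from normal to low or high on a given test.

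**Working it through.** **Step 1. Is every abnormal result an adverse event?** The SAP's premise against the protocol's rules:

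| Source | What becomes an adverse event |
|---|---|
| SAP 3.5 and section 5 | Any abnormal result, without qualification |
| Protocol 8.1.4 | The investigator must "record any clinically relevant changes occurring during the study in the AE section of the CRF" |
| Protocol Appendix 3, events meeting the definition | Abnormal results "considered clinically significant in the medical and scientific judgment of the investigator (ie, not related to progression of underlying disease" |
| Protocol Appendix 3, events not meeting the definition | Excludes even clinically significant findings "which are associated with the underlying disease, unless judged by the investigator to be more severe than expected" |
| Protocol 8.1.3 (ECG) | "Results are to be documented in the eCRF as normal, or abnormal and whether clinically significant" |

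The ECG row shows that the protocol treats being abnormal and being clinically significant as two separate facts. Sites enter adverse events under the protocol, and the SAP cannot widen that afterwards. Two classes of abnormal result therefore never reach the adverse event tables: those judged not clinically significant, and those attributed to the disease and no worse than expected.

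**Step 2. What does the SAP still tabulate by arm?**

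- Laboratory (3.5.2, 3.1.4): n, mean, median, SD, minimum and maximum of values and changes. No category counts, no shifts.
- Adverse events (3.5.1): counts, for results that qualify.
- ECG (3.5.4): counts of overall interpretation.
- Examinations (3.5.5): counts at each visit, no shifts.
- Vital signs (3.5.3): descriptive statistics; change from baseline is not mentioned.

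Low/normal/high laboratory tables by arm: 0. Shift tables by arm: 0.

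**Step 3. How many tests?** Protocol Table 1 lists platelets, red cells, haemoglobin, haematocrit, white cells and 5 differentials = 10. It also lists urea nitrogen, creatinine, potassium, sodium, calcium, AST, ALT, alkaline phosphatase, total bilirubin, direct bilirubin and total protein = 11. Total 21. Scheduled samples are at screening and week 12. Rebuilding all counts from the listing would involve up to 48 × 21 × 2 = 2,016 results, or 40 × 21 × 2 = 1,680 for 40 evaluable patients. For key tests alone the number is smaller.

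**Step 4. Can the count be recovered from the retained statistics?** No. Take 48 × 2/3 = 32 safinamide patients and assumed week-12 values in multiples of the upper limit of normal (ULN):

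- Set A: 0.30 ×1, 0.50 ×14, 0.60 ×6, 0.65 ×4, 1.00 ×6, 1.30 ×1.
- Set B: 0.30 ×1, 0.50 ×9, 0.55 ×3, 0.60 ×13, 1.05 ×5, 1.30 ×1.

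Both have n = 32, sum 20.80 and sum of squares 15.13. Mean = 20.80/32 = 0.65. SD = √[(15.13 − 32 × 0.65²)/31] = √(1.61/31) = 0.228. The median is 0.60, the minimum 0.30 and the maximum 1.30 in both. Set A has 1 patient above ULN (1/32 = 3.1%) and set B has 6 (6/32 = 18.8%). On a 0.05 grid with these six statistics fixed, 1 and 6 are the smallest and largest possible counts.

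If every baseline were 0.60, the change summaries would also agree: mean 0.05, SD 0.228, median 0, minimum −0.30, maximum 0.70. Yet 1 patient in A and 6 in B would have shifted from normal to high.

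**The case against.** The nearest contrary text is the general note in protocol Appendix 3, which says an adverse event can include an abnormal laboratory finding. It describes what may be an adverse event; the list that follows sets the clinical-significance condition. It does not rescue the SAP's premise.

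The stronger objections concern size, and several stand:

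- This is a pilot with descriptive safety analysis, and no decision rule depends on a shift table. All laboratory results are listed, clinically significant abnormal tests are repeated until resolved or no longer significant, and possible Hy's Law events must be reported as serious. What is lost is a table, not data.
- The illustration is constructed. Set A puts six patients at exactly 1.00 × ULN and set B puts five at 1.05, so it shows that summaries do not fix a threshold count, not that a signal is hidden. The equal-baseline extension is artificial, and the SAP does not say it will summarise in ULN multiples.
- The protocol planned the table for key tests only, so 21 is the number of tests measured, not the number of tables lost. The 2,016 is an upper bound: week-12 visits could be remote, and the listing may carry out-of-range flags. Repeat or unscheduled samples are outside this count.
- That a pooled minimum or maximum cannot be read against one limit assumes that local ranges differ. Testing is local (protocol 10.1.4), but the documents give no ranges.

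The separate programming specifications might add flags, but they would not reinstate a table that section 5 withdraws. None of this supplies the comparison by arm that the endpoint asks for.

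**Conclusion.** The concern holds. The reason for dropping the shift tables contradicts the protocol's adverse event definition. As written, the SAP reports neither low/normal/high counts nor shifts by arm for any laboratory test, although the primary objective's endpoint names both shifts and abnormalities. This rests on the text alone and needs no assumed figure. The 3% to 19% range is an illustration on assumed values.

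The practical consequence is moderate: a by-arm view of abnormal results not recorded as adverse events is missing from the tables, though it could be rebuilt if the ranges are held. The plan should be corrected, but the trial's safety data are not compromised.

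Two lesser points belong alongside. The examination shift table falls with the same sentence, although counts by visit remain. Separately, protocol 9.4.1.3 requires vital-sign change from baseline; SAP 3.5.3 does not mention it and section 5 declares no such change.

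**What to change.** 1. Delete the shift-table sentence in SAP section 5.
2. In SAP 3.5.2, restore the table by arm of low/normal/high categories, baseline to week 12. Name the key tests and classify each result by the range of the local laboratory that produced it.
3. Reword SAP 3.5 so that only abnormalities meeting the protocol's adverse event definition are said to be reported as adverse events.
4. Secondary: restore the examination shift table, state vital-sign change from baseline in SAP 3.5.3, and align the laboratory endpoint wording in SAP 2.3.2 with protocol section 3.

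A lighter alternative is to correct the reason and add out-of-range counts by arm. That would cover the occurrence of abnormalities but not shifts, so the full table is preferable.

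The cost is some SAP text and two tables the protocol already specified, each with one baseline and one later time point. The uncertain item is the normal ranges: the documents do not say they are in the database. Confirm this first; if they are absent, collecting them from local laboratories would be the main expense.
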